7.1.2 Treatment Period

7.1.2.2 Study Procedures: After enrollment and prior to vaccination

- PNOC Health Related Quality of Life & Neurocognitive Measures (+7 days after registration; see Appendix H) – for Stratum C only.
- Brain MRI; spine MRI only if clinically indicated within 14 days of treatment start.

7.1.2.3 Study Procedures Day 1 of Week 0 (all strata, unless otherwise indicated)

Laboratory assessments do not need to be repeated if completed within 7 days prior.

Prior to Vaccination:

- Baseline toxicity assessment including assessment of any residual toxicity relating to prior radiation therapy.
- Physical examination including neurological examination
- Vital signs
- Pulse oximetry (Stratum C only)
- Performance status
- Concomitant medications
- CBC with differential and platelet count
- Blood chemistry assessment, including:
 - ALT/AST, total bilirubin, calcium, phosphorus, BUN, creatinine, albumin, glucose, potassium, sodium, chloride, bicarbonate
 - Lipase, amylase, and CRP (Stratum C only)
 - CPK and cardiac troponins (Stratum C only)
- TSH (if TSH is abnormal also measure free T4) (Stratum C only)
- Urine analysis (UA) (Stratum C only)
- Correlative immune monitoring assessments
- Circulating tumor DNA
- Serum or urine pregnancy test for females of childbearing age (within 24 hours prior to the initial administration of study drug)

Vaccination:

• Vaccination with K27M/TT

• IM injection of poly-ICLC (if evidence of pseudo-progression after radiation therapy on Eligibility MRI, poly-ICLC can be held for up to 12 weeks)

Post Vaccination:

• All patients will be closely observed for adverse events for at least 20 minutes following each vaccination. Any time thereafter, patients should report any adverse events to the research coordinator or research clinician.

Nivolumab (+/- 3 days; Stratum C only):

• Infusion of nivolumab on the same day as K27M/TT vaccination and poly-ICLC injection or within 3 days (+/- 3 days) of vaccination. Infusion can occur before or after vaccination.

7.1.2.4 Study Procedures Day 1 of Weeks 3, 6, 9, 12, 15, 18, 21 (- 3 days) (all strata, unless otherwise indicated)

Laboratory assessments do not need to be repeated if completed within 7 days prior.

Prior to vaccination:

- Physical examination including neurological examination
- Vital signs
- Pulse oximetry (Stratum C only)
- Performance status
- Evaluation of adverse events
- Concomitant medications
- CBC with differential and platelet count
- Blood chemistry assessment, including:
 - Alkaline phosphatase, ALT/AST, total bilirubin, calcium, phosphorus, BUN, creatinine, total protein, albumin, glucose, potassium, sodium, and chloride, bicarbonate
 - Lipase, amylase, and CRP (Stratum C only)
 - CPK and cardiac troponins (Stratum C only)
- TSH (if TSH is abnormal also measure free T4) (Stratum C only)
- UA (Stratum C only)
- Serum or urine pregnancy test for females of childbearing age
- ECHO and ECG, as clinically indicated (Stratum C only)

Vaccination:

- Vaccination with K27M/TT
- IM injection of poly-ICLC

Post Vaccination:

• All patients will be closely observed for adverse events for at least 20 minutes following each vaccination. Any time thereafter, patients should report any adverse events to the research coordinator or research clinician.

Nivolumab (+/- 3 days; Stratum C only):

Infusion of nivolumab on the same day as K27M/TT vaccination and poly-ICLC injection or within 3 days (+/- 3 days) of vaccination. Infusion can occur before or after vaccination.

7.1.2.5 Study Procedures Day 1 of Week 24 (- 3 days)

Laboratory assessments do not need to be repeated if completed within 7 days prior.

- Physical examination including neurological examination
- Vital signs
- Pulse oximetry (Stratum C only)
- Performance status
- Evaluation of adverse events
- Concomitant medications
- CBC with differential and platelet count
- Blood chemistry assessment, including:
 - Alkaline phosphatase, ALT/AST, total bilirubin, calcium, phosphorus, BUN, creatinine, total protein, albumin, glucose, potassium, sodium, chloride, and bicarbonate
 - Lipase, amylase, and CRP (Stratum C only)
 - CPK and cardiac troponins (Stratum C only)
- TSH (if TSH is abnormal also measure free T4) (Stratum C only)
- UA (Stratum C only)
- Serum or urine pregnancy test for females of childbearing age
- Echo/ECG, as clinically indicated (Stratum C only)

Nivolumab (+/- 3 days; Stratum C only)

7.1.2.6 Study Procedures Day 1 of Week 27, 30, 33, 36, 39 etc. through Week 96 (- 3 days)

Laboratory assessments do not need to be repeated if completed within 7 days prior.

Stratum C only

- Physical examination including neurological examination
- Vital signs

- Pulse oximetry
- Performance status
- Evaluation of adverse events
- Concomitant medications
- CBC with differential and platelet count
- Blood chemistry assessment, including:
 - Alkaline phosphatase, ALT/AST, total bilirubin, calcium, phosphorus, BUN, creatinine, total protein, albumin, glucose
 - Lipase, amylase, and CRP
 - CPK and cardiac troponins
- TSH (if TSH is abnormal also measure free T4)
- UA
- Serum or urine pregnancy test for females of childbearing age
- Echo/ECG, as clinically indicated (Stratum C only)

Nivolumab (+/- 3 days; Stratum C only)

Vaccination (every 6 weeks, weeks 27, 33, 39, 45, 51, 57, 63, etc. through Week 96:

- Vaccination with K27M/TT
- IM injection of poly-ICLC

Post Vaccination:

- All patients will be closely observed for adverse events for at least 20 minutes following each vaccination. Any time thereafter, patients should report any adverse events to the research coordinator or research clinician.
- 7.1.2.7 Study Procedures Day 1 of Weeks 12, 24, 36, 48, 60, 72, 84, 96 (- 7 days) (All strata)

Laboratory assessments do not need to be repeated if completed within 7 days prior.

- Brain MRI (-14 days)
- Spine MRI if clinically indicated (-14 days)
- Circulating tumor DNA
- Immuno-monitoring assessments (also to be collected at Week 18)

7.1.3 Every 3 months (+/- 14 days)

• PNOC Health Related Quality of Life & Neurocognitive Measures (PEDs-QL, PROMIS, and ADHD; see Appendix H) – Stratum C only.

7.1.4 Every 6 months for two years then every 12 months after two years, while on treatment (+/- 14 days)

 PNOC Health Related Quality of Life & Neurocognitive Measures (ABAS-3 and BRIEF; see Appendix H) – Stratum C only.

7.1.5 End-of-Treatment Study Procedures (-14 days) (all strata, unless otherwise indicated)

The following assessments should be completed on the last day of treatment if not assessed within 14 days prior.

- Evaluation of clinical response or deterioration (including MRI, if MRI not done within 30 days prior)
- Physical examination including neurological examination
- Vital signs
- Pulse oximetry (Stratum C)
- Performance Status
- Evaluation of adverse events; all Adverse Events (AEs) that occur following the subject's written consent to participate in the study through 100 days of discontinuation of dosing, whether related or not related to study drug will be recorded.
- Concomitant medications
- CBC with differential and platelet count
- Blood chemistry assessment, including:
 - Alkaline phosphatase, ALT/AST, total bilirubin, calcium, phosphorus, BUN, creatinine, total protein, albumin, glucose, potassium, sodium, chloride, and bicarbonate
 - Lipase, amylase, and CRP (Stratum C only)
 - CPK and cardiac troponins (Stratum C only)
- TSH (if TSH is abnormal also measure free T4) (Stratum C only)
- UA (Stratum C only)
- Serum or urine pregnancy test for females of childbearing age
- ECHO/ECG, as clinically indicated (Stratum C only)
- PNOC Health Related Quality of Life & Neurocognitive Measures (see Appendix H) (Stratum C only)

Vaccination (if last day of treatment):

- Vaccination with K27M/TT
- IM injection of poly-ICLC

Post Vaccination:

• All patients will be closely observed for adverse events for at least 20 minutes following each vaccination. Any time thereafter, patients should report any adverse events to the research coordinator or research clinician.

Nivolumab (+/- 3 days; Stratum C only):

• Infusion of nivolumab on the same day as K27M/TT vaccination and poly-ICLC injection or within 3 days (+/- 3 days) of vaccination. Infusion can occur before or after vaccination.

7.1.6 30 Day Toxicity Check

To be completed 30 days (+7 days) after last day of treatment; this may be done by telephone contact.

- Evaluation of adverse events (All study drug related adverse events must continue to be followed until resolution or return to baseline).
- Review of concomitant medications
- 7.1.7 Every 12 months during Follow-up (+/- 14 days)
 - PNOC Health Related Quality of Life & Neurocognitive Measures (PEDs-QL, PROMIS, ADHD, ABAS-3 and BRIEF; see Appendix H) Stratum C only.

7.1.8 Long Term/Survival Follow-up Procedures

Subjects in the follow up phase will be followed by chart review and/or telephone contact until an offstudy criterion is met to collect survival information (including disease status and any new treatment started) every three months (+/- 2 weeks) for 24 months. Any study drug related adverse events will be followed until resolution or return to baseline. PNOC Health Related Quality of Life & Neurocognitive Measures will also be collected according to the schedule delineated in Appendix H for patients enrolled in Stratum C only.

The requested follow-up data is to be submitted quarterly from the date the patient went off treatment. This information will be recorded in Advarra® eCRFs due at Follow-up.

7.2 Off Study Criteria

Subjects will be considered Off Study for the following reasons:

- Subject determined to be ineligible.
- Parent, subject, or guardian withdraws consent for continued participation.
- Subject death while on study.

Subjects who expire without confirmation of disease status will be considered progressive disease at the time of death.

The date and reason for the subject coming off study must be documented in the 'Follow-Up' section of OnCore® as well as the 'PNOC End of Treatment eCRF' in Advarra®. No data will be collected after the "off study" date.

Table 6.1 Schedule of Study Procedures and Assessments (Strata A and B)

Study Day/Visit	Eligibility (-14 days) ¹	Day 1 on Weeks 0, 3, 6, 9, 12, 15, 18, 21, 24 (-3 days)	Day 1 on Weeks 30, 36, 42, 48, 54, 60, 66, 72, 78, 84, 90, 96 (-3 days) ²	End of Treatment Visit (-14 days) ³	30 Day Toxicity Check (+7 days)⁴	Follow- Up⁵
Clinical procedures						
HLA typing	X6					
H3.3K27M mutation status	X6					
Consent Form	X1					
Physical Exam ⁷		х	х	Х		
Vital Signs		х	х	Х		
Medical History ⁸	Х					
Performance Status	х	х	х	х		
Adverse Event assessment		X٩	Х	х	х	х
Concomitant Medications	х	Х	Х	Х	х	
Vaccination ¹⁰ Vaccine Poly-ICLC¹¹ 		Х				
Evaluation of clinical response				х		
Survival⁵						x
Laboratory procedures						
CBC w/ Diff + plts	х	X ¹²	X ¹²	X ¹²		
Blood Chemistry	X ¹³	X ^{12,13}	X ^{12,13}	X ^{12,13}		
Pregnancy test ¹⁴	х	х	Х	х		
Imaging procedures						
Brain MRI/Spine MRI	X ¹⁵	X ¹⁵	X ¹⁵	X ^{4,15}		
Specimen Collection						
Immune monitoring tests ¹⁶		х	Х			
Blood for ctDNA 17		x	Х			
Tumor Tissue Collection ¹⁸			Х			

- 1. Eligibility tests and procedures must be performed within 14 days prior to enrollment. Consent to study therapy must be signed.
- If the subject demonstrates no evidence of disease progression and tolerates the therapy well (defined as not having any regimen related toxicities (RLT); see Section 6.3) after the 8th dose (Week 21), patients may receive additional vaccinations starting at Week 30, every 6 weeks, for a total of 96 weeks (approximately 2 years).
- 3. End of treatment procedures to occur on last day of treatment. These do not need to be repeated if occurred within 14 days prior. Brain/Spine MRI to be repeated if not done within 30 days prior to the end of treatment visit.
- 4. 30-day toxicity check may be done via telephone if needed (+7 days). Related AEs must continue to be followed until resolution or return to baseline
- 5. Subjects in the follow up phase will be followed by chart review and/or telephone contact until an off- study criterion is met to collect survival information every three months for 24 months.
- Subjects must be positive for HLA-A2 and H3.3K27M. HLA A*02:01 typing (based on sequencing) and H3.3K27M mutation status must be done in a CLIA- or equivalent approved laboratory. If H3.3K27M mutation analysis is to be performed at UCSF, pathology and imaging (MRI), and tissue must be submitted.
- 7. To include neurological exam.
- 8. To include history of prior treatments and any residual toxicity relating to prior radiation therapy and baseline conditions assessment.
- 9. Adverse assessments to be assessed at all visits following Week 0 vaccine administration.
- 10. All patients will be closely observed for adverse events for at least 20 minutes following each vaccination. Vaccine will not be administered on Week 24 or Week 27. Vaccination will resume on Week 30 and every 6 weeks thereafter, for a total of 96 weeks (approximately 2 years).
- 11. If there is evidence of pseudo-progression after radiation therapy on baseline MRI, poly-ICLC can be held for up to 12 weeks.
- 12. Laboratory assessments do not need to be repeated if completed within 7 days prior.
- 13. Blood chemistry to include: At screening: aspartate aminotransferase/alanine aminotransferase (ALT/AST), total bilirubin, creatinine and albumin. Week 0 and beyond: alkaline phosphatase, aspartate aminotransferase/alanine aminotransferase (ALT/AST), total bilirubin, calcium, phosphorus, blood urea nitrogen (BUN), creatinine, total protein, albumin, glucose, potassium, sodium, chloride, bicarbonate.
- 14. May be serum or urine pregnancy test; for females of child-bearing potential.
- 15. Spinal MRI only required if clinically indicated. Post radiation therapy MRI must occur within 14 days of enrollment and within 14 days of treatment start date (Day 1 Week 0). MRI(s) to be obtained at baseline and then every 12 weeks thereafter (-14 days) at Weeks 12, 24, 36, 48, etc.
- 16. To be obtained at weeks 0 (prior to vaccine), 12, 18, and 24 and then every 12 weeks thereafter each time a MRI is performed (-7 days) (i.e. Week 36, 48, 60, etc.). See Section 9 for further details.
- 17. To be obtained at baseline (Week 0 Day 1) and then every 12 weeks (-7 days).
- 18. If a patient has evidence of progressive disease and is undergoing tumor tissue resection as part of standard of care, a sample should be sent to UCSF for further analysis to assess antigen loss and immune cell infiltration. Please see Section 9.2.2 for further details. Please refer to PNOC SharePoint member website for shipping information.

Table 6.2 Schedule of Study Procedures and Assessments (Stratum C)

Study Day/Visit	Eligibility (-14 days) ¹	Day 1 on Weeks 0, 3, 6, 9, 12, 15, 18, 21, 24, 27, 33, 39, 45, 51, 57, 63, 69, 75, 81, 87, 93, and 96 (-3 days) ²	End of Treatment Visit (-14 days) ³	30 Day Toxicity Check (+7 days) ⁴	Follow-Up⁵
Clinical procedures					
HLA typing	X6				
H3.3K27M mutation status	X6				
Consent Form	x				
Physical Exam ⁷		x	Х		
Vital Signs		X	Х		
Pulse oximetry	Х	Х	Х		
Medical History ⁸	Х				
Performance Status	x	Х	Х		
Adverse Event assessment ⁹	x	Х	Х	х	x
Concomitant Medications	x	х	х	х	
Drug administration • Vaccine ¹⁰ • Poly-ICLC ¹¹ • Nivolumab ²⁰ (every 3 weeks through 96 week study)		x	х		
Evaluation of clinical response			х		
Survival ⁵					x
Laboratory procedures					
CBC w/ Diff + plts	Х	X ¹²	X ¹²		
Blood Chemistry	X ¹³	X ^{12,13}	X ^{12,13}		
Pregnancy test ¹⁴	x	x	х		
Urinalysis	X	X	X		
CPK & cardiac troponins		x	х		
Imaging/cardiology procedures					
ECG ¹⁵		Х	х		

ECHO ¹⁵		Х	х	
Brain MRI/Spine MRI	X ¹⁶	X ¹⁶		
Quality of Life Assessments				
QOL Assessments(see Appendix H for specific timepoints)	х	Х	х	х
Specimen Collection				
Immune monitoring tests ¹⁷		Х		
Blood for ctDNA 18		Х		
Tumor Tissue Collection ¹⁹	х			

- 1. Eligibility tests and procedures must be performed within 14 days prior to enrollment. Consent to study therapy must be signed. H3.3K27M sequencing and HLA typing may be done prior to 14 days within enrollment.
- 2. If the subject demonstrates no evidence of disease progression and tolerates the therapy well (defined as not having any regimen related toxicities (RLT); see Section 6.3) after the 8th dose (Week 21), patients may continue to receive nivolumab every 3 weeks after the 8th dose for a total of 96 weeks. Patients may receive additional vaccination with K27M/TT and poly-ICLC combined with nivolumab every 6 weeks after the 8th dose (starting at Week 27) for a total of 96 weeks.
- 3. End of treatment procedures to occur on last day of treatment. These do not need to be repeated if occurred within 14 days prior. Brain/Spine MRI to be repeated if not done within 30 days prior to the end of treatment visit.
- 4. 30-day toxicity check may be done via telephone if needed (+7 days). Related AEs must continue to be followed until resolution or return to baseline
- 5. Subjects in the follow up phase will be followed by chart review and/or telephone contact until an off-study criterion is met to collect survival information every three months for 24 months.
- Subjects must be positive for HLA-A*02:01 and H3.3K27M. HLA A*02:01 typing (based on sequencing) and H3.3K27M mutation status must be done in a CLIA- or equivalent approved laboratory. If H3.3K27M mutation analysis is to be performed at UCSF, pathology and imaging (MRI), and tissue must be submitted.
- 7. To include neurological exam.
- 8. To include history of prior treatments and any residual toxicity relating to prior radiation therapy and baseline conditions assessment.
- 9. Adverse assessments to be collected following the subject's written consent to participate in the study through 100 days of discontinuation of dosing, whether related or not related to study drug.
- 10. All patients will be closely observed for adverse events for at least 20 minutes following each vaccination. Vaccine will not be administered on Week 24. Vaccination will resume on Week 27 and every 6 weeks thereafter, for a total of 96 weeks (approximately 2 years).
- 11. If there is evidence of pseudo-progression after radiation therapy on baseline MRI, poly-ICLC can be held for up to 12 weeks.
- 12. Laboratory assessments do not need to be repeated if completed within 7 days prior.
- 13. Blood chemistry to include: At screening: aspartate aminotransferase/alanine aminotransferase (ALT/AST), total bilirubin, creatinine, albumin, lipase, amylase, C-reactive protein (CRP), and TSH. Week 0 and beyond: alkaline phosphatase, aspartate aminotransferase/alanine aminotransferase (ALT/AST), total bilirubin, calcium, phosphorus, blood urea nitrogen (BUN), creatinine, total protein, albumin, glucose, potassium, sodium, chloride, bicarbonate, lipase, amylase. CRP, TSH (if TSH is abnormal also measure free T4), urine analysis (UA).

- 14. Required within 24 hours prior to the initial administration of nivolumab, then every 3 weeks. May be serum or urine pregnancy test; for females of child-bearing potential.
- 15. Day 1, each visit starting at Week 3 (excluding Week 24): as clinically indicated. **End of Treatment**: as clinically indicated.
- 16. Spinal MRI only required if clinically indicated. Post radiation therapy MRI must occur within 14 days of enrollment and within 14 days of treatment start date (Day 1 Week 0). MRI to be obtained at baseline and then every 12 weeks thereafter (-14 days) at Weeks 12, 24, 36, 48, etc.
- 17. To be obtained at weeks 0 (prior to vaccine), 12, 18, and 24 and then every 12 weeks thereafter each time a MRI is performed (-7 days) (i.e. Week 36, 48, 60, etc.). See Section 9 for further details.
- 18. To be obtained at baseline (Week 0 Day 1) and then every 12 weeks (-7 days).
- 19. If a patient has evidence of progressive disease and is undergoing tumor tissue resection as part of standard of care, a sample should be sent to UCSF for further analysis to assess antigen loss and immune cell infiltration. Please see Section 9.2.2 for further details. Please refer to PNOC SharePoint member website for shipping information.
- 20. Nivolumab to be given every 3 weeks. Nivolumab will be given IV before or after vaccine and poly-ICLC injection (+/- 3 days of vaccination and poly-ICLC injection).

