4.1 General Guidelines

Participant must meet all inclusion criteria and no exclusion criteria should apply. The participant or their legal parent/guardian must have signed and dated an approved, current version of the applicable consent and/or assent forms. To allow non-English speaking participants to participate in this study, bilingual health services will be provided in the appropriate language when feasible.

The treating physician must complete and sign the eligibility checklist. A clinical team member (nurse or clinical research coordinator) must also sign. The completed eligibility checklist will be submitted to the PNOC Operations Office for review. The PNOC Operations Office will review the eligibility checklist to ensure that all items on the eligibility checklist are filled out.

Eligible participants will be registered using the UCSF OnCore® database. Treatment on protocol therapy cannot be initiated prior to receiving the registration confirmation email from the PNOC Operations Office.

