9.6 Recording of an Adverse Event

All clinically significant adverse events will be entered into Advarra[®], whether or not the event is believed to be associated with use of the study drug. Data about these events and their severity will be recorded using the NCI CTCAE v5.0. All clinically significant Adverse Events (AEs) that occur following the subject's written consent to participate in the study through 100 days of discontinuation of dosing must be reported, whether related or not related to study drug.

The Investigator will assign attribution of the possible association of the event with use of the investigational drug, and this information will be entered into Advarra[®] using the classification system listed below:

Relationship	Attribution	Description
Unrelated to investigational drug/intervention	Unrelated	The AE is clearly NOT related to the intervention
	Possible	The AE may be related to the intervention
Related to investigational drug/intervention	Probable	The AE is likely related to the intervention
0	Definite	The AE is clearly related to the intervention

,Signs or symptoms reported as adverse events will be graded and recorded by the Investigator according to the CTCAE. When specific adverse events are not listed in the CTCAE they will be

graded by the Investigator as *none*, *mild*, *moderate* or *severe* according to the following grades and definitions:

Grade 0	No AE (or within normal limits)
Grade 1	Mild; asymptomatic or mild symptoms; clinical or diagnostic observations only; intervention not indicated
Grade 2	Moderate; minimal, local, or noninvasive intervention (e.g., packing, cautery) indicated; limiting age-appropriate instrumental activities of daily living (ADL)
Grade 3:	Severe or medically significant but not immediately life-threatening; hospitalization or prolongation of hospitalization indicated; disabling; limiting self- care ADL
Grade 4:	Life-threatening consequences; urgent intervention indicated

Grade 5: Death related to AE

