10.3.1 Analysis Population

Intent-to-Treat Population (ITT): The ITT population will include all subjects who are enrolled in the study. The ITT population will be the primary population for evaluating efficacy and subject characteristics.

As-Treated Population (AT) The AT population will include all subjects who receive at least 1 course of study therapy. The AT population will be the primary population for evaluating safety. If a patient does not receive any vaccine and poly-ICLC (strata A and B) in combination with nivolumab (stratum C), they will be replaced for evaluation of safety.

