10.3.2 Analysis of Primary Endpoints

- Safety of K27M/TT vaccine and poly-ICLC in combination with nivolumab (stratum C only) will be assessed by monitoring for adverse events, scheduled laboratory assessments, vital sign measurements, and physical examinations for subjects who receive at least one course of the study therapy. The severity of toxicities will be graded according to the NCI CTCAE v5.0. Adverse events and will be summarized by maximum intensity and relationship to study drug(s).
- Safety will be assessed every 3 weeks for the first 24 weeks and then every 6 weeks. Descriptive statistics will be utilized to display the data on toxicity seen.
- OS12 in HLA-A02:01⁺ children with H3.3K27M positive DIPG (Stratum A) will be the clinical efficacy primary endpoint. Any subject enrolled (ITT) will be considered evaluable for clinical efficacy. Patients lost to follow-up before 12 months will be considered events and the OS probability at 12 months (OS12) will be estimated from the Kaplan-Meier method. Two-sided 95% CI will be computed based on the Greenwood's formula.

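### A child found ineligible after enrollment goes off study with no further data, against the 100-day adverse-event rule and the all-enrolled OS12 analysis

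*Combined protocol and SAP*

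**What the plan says.** Section 7.2 gives three off-study reasons: ineligibility ("Subject determined to be ineligible"), withdrawal of consent, and death on study. The first carries no time limit. The section closes with "No data will be collected after the" off-study date. Section 7.1.8 continues survival contact only "until an offstudy criterion is met to collect survival information", and footnote 5 of Tables 6.1 and 6.2 says the same.

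The reporting and analysis sections make no exception for ineligible subjects:

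- Section 9.6 covers clinically significant adverse events from consent "through 100 days of discontinuation of dosing must be reported, whether related or not related to study drug". Section 7.1.5 sets the same window for all adverse events, and sections 9.9 and 9.10.4 set it for serious adverse events.
- Section 10.3.1: "The ITT population will include all subjects who are enrolled in the study". The as-treated set, used for safety, takes in everyone who received at least one course.
- Section 10.3.2 treats every enrolled subject as evaluable for efficacy and adds: "Patients lost to follow-up before 12 months will be considered events".

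**The concern.** The ineligibility criterion does not separate a screen failure from a child who has been enrolled, or enrolled and dosed. Applied as written to a dosed child, it stops the site from collecting safety data that other sections make mandatory. Applied to any enrolled child, it stops collection of the vital status on which OS12 depends, while the child stays in the analysis set.

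Late findings are possible. Under section 4.1 the central office "will review the eligibility checklist to ensure that all items on the eligibility checklist are filled out", which is a completeness check. Some relevant assessments also fall after enrollment: the MRI between enrollment and vaccination (section 7.1.2.2) and the pregnancy test within 24 hours before first dosing (section 7.1.2.3). Disseminated disease and pregnancy are both exclusions in section 3.2.2.

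At stake are the completeness of the safety data in a stratum of 20, and an agreed way to count such a child in OS12.

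**Working it through.** **Safety data.** Take a dosed child found ineligible d days after the last dose, with no further dosing. Section 7.2 forbids data from day d onward. Sections 7.1.5, 9.6, 9.9 and 9.10.4 require capture to day 100. The required reporting that is lost is 100 − d days: all 100 if the finding falls on the day of the last dose, 60 if d = 40. No section says which rule prevails.

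**Survival data.** Section 7.1.8 and footnote 5 end survival contact at any off-study criterion, and ineligibility is one. Sections 10.3.1 and 10.3.2 keep the child in the efficacy set. Membership is not in conflict, but the outcome is no longer collected.

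**Which stratum is affected now.** Section 5.1.5 reports 29 patients treated by 12/31/18, 19 in Stratum A and 10 in Stratum B, which are the full targets. Section 1.3 gives a safety cutoff of September 8, 2020 and describes the current amendment as the one that adds nivolumab. That is more than 20 months after the last Stratum A child was counted as treated, and section 9.3.1.4 measures survival from diagnosis. Month 12 had therefore passed for all of Stratum A before this version. The change can act prospectively in Stratum C. There, section 10.1.1 names safety as the only primary endpoint and section 10.1.2 lists OS12 as exploratory (section 10.2.1 calls it secondary).

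**Illustration for Stratum A scoring.** Section 10.2.1 gives n = 19, null OS12 40%, alternative 70%, and rejection when at least 12 are alive.

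The planned test, with X ~ Binomial(19, p):

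- Alpha = P(X ≥ 12 | p = 0.40) = 0.0352, against 3.5% stated.
- Power = P(X ≥ 12 | p = 0.70) = 0.818, against 80% stated.

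The plan's figures are reproduced. Now let k living children be taken off study before month 12 and counted as events. At most 19 − k can be counted alive, so X ~ Binomial(19 − k, p) with the cutoff still at 12. The values of k are assumed.

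| k | Alpha | Power at 70% |
|---|---|---|
| 0 | 3.52% | 81.8% |
| 1 | 2.03% | 72.2% |
| 2 | 1.06% | 59.7% |

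Each such child lowers the observed proportion by 1/19 = 5.3 points.

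If the k children are dropped instead, and the cutoff is the smallest with exact alpha at most 5%:

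| n | Cutoff | Alpha | Power at 70% |
|---|---|---|---|
| 18 | 12 | 2.03% | 72.2% |
| 17 | 11 | 3.48% | 77.5% |

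With one child, the two conventions give the same alpha and power. With two they differ, so the convention needs to be stated.

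**The case against.** The best defence is that the criterion means screen failures only. Consented patients enter OnCore before the eligibility checklist is complete (sections 4.2 and 7.1), so some route off study is needed for them. The checks before treatment are also more than clerical: the treating physician and a second team member sign the checklist, and certified-laboratory results for HLA-A*02:01 and H3.3K27M are inclusion criteria. This supports the view that late findings will be rare. It does not settle the meaning. Section 7.2 never limits the criterion, lists it beside death on study, and asks for the reason on the End of Treatment form, which suits subjects already on study.

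A second defence is that the specific safety rules would override a general closing sentence. Section 9.7 does foresee follow-up after removal from study, but only for unacceptable adverse events. A sensible site might read the rules that way, but the protocol does not say so.

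A reader might infer three stronger things that the documents do not support:

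- That a treated child's toxicity vanishes from the safety endpoint. Events before the off-study date stay recorded, and a child who received at least one course stays in the as-treated set. Only later events are at risk.
- That the plan scores a living ineligible child as dead. Section 10.3.2 speaks of patients lost to follow-up and does not say that removal for ineligibility counts as loss.
- That Stratum A stands to lose power which a new rule would protect. Its children were treated and past month 12 before this version.

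**Conclusion.** The contradiction is in the text and depends on no calculation. For a dosed child later found ineligible, a site cannot follow section 7.2 and the 100-day rules together. For any enrolled child, section 7.2 cuts off the outcome that the all-enrolled OS12 analysis needs.

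The case should be rare, and the documents give no frequency. The main prospective consequence is incomplete safety data in Stratum C. For Stratum A the open question is only how any such child is scored. The fall in power from 81.8% to 72.2% is an illustration: it assumes exactly one such child, alive when removed, counted as an event, with the other 18 at 70%. Under that scoring alpha falls as well, so the error is conservative. The point merits an amendment because following section 7.2 as written loses required data and the repair is cheap.

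**What to change.** - **Section 7.2, criterion.** Limit ineligibility as an off-study reason to consented subjects who were never enrolled (screen failures).
- **Section 7.2, enrolled subjects.** State that an enrolled subject later found ineligible is recorded as a protocol deviation and, unless consent is withdrawn, remains in follow-up for data collection only. If dosed, collect adverse and serious adverse events through 100 days after the last dose. Dosed or not, continue the quarterly survival contact of section 7.1.8 at least to 12 months.
- **Consistency.** Amend the closing sentence of section 7.2 to match, and align section 7.1.8 and footnote 5 of Tables 6.1 and 6.2. Changing the criterion alone would leave the bar on data in place.
- **Sections 10.2.1 and 10.3.2.** Score OS12 from actual vital status wherever it is known, including for any such Stratum A child. Apply the lost-to-follow-up rule only when status cannot be obtained.

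The cost is a few sentences and, for very few subjects, extra telephone or chart contacts of a kind section 7.1.8 already provides. The change concerns data collection only and says nothing about whether treatment continues.
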